A non-surgical treatment option for the management of osteoarthritis include injectables such as corticosteroids and platelet rich plasma (PRP). These injectables work by positively affecting cartilage cells, also known as chondrocytes, and the cells of the joint lining tissue, also known as synoviocytes. PRP is an autologous derived blood product, i.e. a joint injectable made from the patient's own blood at the time and location of injection with simple blood centrifugation. Studies in the bench-top laboratory setting have provided in-vitro evidence that PRP decreases synoviocyte production of metalloproteinases, an inflammatory protein with negative effects on cartilage, decreases the effects of inflammatory proteins such as IL-6 on chondrocytes, and has an anti-inflammatory effect upon the gene expression of chondrocytes and synoviocytes[14-16]. While these are mechanisms that can help manage osteoarthritis after it arises, they also are mechanisms that could help prevent osteoarthritis before it forms. Recent comparative studies of PRP to other injectables in the management of osteoarthritis suggest a greater, long-lasting effect of PRP than other injectables [1-6].

Orthopedic research has focused on methods to prevent PTOA after ACL injury. Recent study involving the post-injury ACL joint milieu suggested that an early intervention of joint aspiration and corticosteroid injection has positive effects, including a decrease in biomarkers responsible for chondral degeneration [13]. This combined with in vitro study on the effects of PRP on chondrocyte and synoviocyte activity suggest that PRP has potential to affect the ACL-injured joint. However, current literature is lacking in regard to this assertion, and in vivo study of PRP to positively affect the joint after following ACL injury is warranted.

2 Objectives

The main objective of this study is to determine if an early intervention of joint aspiration and PRP injection will positively affect the biomarkers representative of chondral degeneration in patients with ACL injuries. We hypothesize that the intervention will reduce the volume of inflammatory and chondrodegenerative biomarkers following ACL injury.

3 Participant Eligibility

Inclusion Criteria: Patients between the ages of 14 and 40 years with closed growth plates as visualized on plain radiography, no history of previous traumatic ipsilateral knee injury, and no

Effect of Platelet Rich Plasma Injections on Inflammatory and Chondrodegenerative Biomarkers in Patients with Acute Anterior Cruciate Ligament Tears

[name].

Page 3 of 7

clinical evidence of posterior cruciate ligament injury with no more than grade 1 medial or lateral collateral ligament injury.

Exclusion criteria: Patients without a palpable knee effusion, an injury occurring more than 10 days before enrollment, previous ipsilateral knee surgery, intra-articular cortisone or PRP injection into either knee within 3 months of injury, participation in another clinical drug trial within the 4 weeks before injury, and a history of any inflammatory disease or immune-comprised. Any patient who will have difficulty obtaining internet access, does not have an active e-mail address, or is unable to comprehend study documents or give informed consent will be excluded.

4 Participant Enrollment

60 patients will be recruited through the Andrews Institute physician practices. Potential participants will be prescreened for inclusion and exclusion criteria through standard of care medical evaluations. Once a potential participant has agreed to be involved in the study, they will go through the described informed consent process. Patients meeting the inclusion criteria will have the study explained to them by one of the members of the investigating team, and they will be given an opportunity to participate if they are interested. No specific advertising or recruitment material will be utilized.

The participants will then be randomly placed in one of the two study groups and be scheduled to receive either an injection of PRP or no injection in their involved knee.

Participants will not be billed for the joint aspirations or PRP injections.

5 Study Design and Procedures

Study design will be randomized control trial. Participants who meet the inclusion criteria will have the study explained in detail and informed consent will be obtained as outlined above.

Patients will be randomized to 1 of 2 groups. Both groups will have joint aspirations performed at an initial visit, within the first 10 days after injury, and at the time of surgery, within 4 weeks of injury. Group 1 will receive only joint aspirations as outlined above. Group 2 will undergo aspirations as outlined above and also receive a PRP injection at the initial visit and at a second visit 5-12 days after the initial visit. Joint aspirations and injections will be performed through the superolateral, suprapatellar approach. Patients will be instructed not to take any prescription or over-the-counter nonsteroidal anti-inflammatory medications. Patients will be encouraged to rest, ice, and elevate their injured knee.

Effect of Platelet Rich Plasma Injections on Inflammatory and Chondrodegenerative Biomarkers in Patients with Acute Anterior Cruciate Ligament Tears

[name].

Page 4 of 7

PRP Manufacturing: PRP preparation will involve Autologous Conditioned Plasma disposables (Arthrex, Naples, FL, USA), a commercially available kit for the production of PRP.

Preparation will follow the manufacturer's instructions. The treating physician will then inject the PRP into the involved knee joint following standard aseptic technique per the physician's standard of care. This entire process will be completed in a single patient visit. A 0.1-0.5 mL sample of the PRP will be inserted into a vacutainer for analysis of cell count. Any unused portion of a sample in the physician's office will be disposed of through standard biohazard waste disposal systems as required by law.

Biomarker Analysis: Samples will be prepared and frozen at -80° C until all study sample have been obtained. Enzyme-linked immunosorbent assay kits will be used to assess chondrodegenerative & synovial fluid biomarkers.

6 Expected Risks and Benefits

Risks and Discomforts: Potential risks include those expected with any injection including syncope, dizziness, headache, nausea, tachycardia, infection (septic arthritis, phlebitis, and osteomyelitis), bleeding, or pain. Additionally, participants may experience knee stiffness or inflammation associated with the PRP injection. Knee aspiration and injection are standard medical procedures used routinely in the management of knee osteoarthritis and acute injury. As with any research involving patients there is the inherent risk of a breach in patient confidentiality though this will be minimized through the use of participant code numbers and adherence to all HIPAA guidelines.

Benefits: Direct benefits of the study include potential pain relief, improvement of knee function from joint aspiration, and the potential to decrease the risk of PTOA after ACL injury. It is also believed that the information obtained in this study will help advance treatment of PTOA through the use of regenerative medicine.

7 Data Management Procedures

All personal information is strictly confidential and no names will be disclosed except as required by law. All information and data collected during this research will be recorded in REDCap and exported into a spreadsheet. This spreadsheet will not contain protected health information. The spreadsheet will be stored in a secure password protected folder on a laptop that only the study Investigators will have access to and will be permanently deleted following publication of any and all manuscripts, if any, written as a result of this research. Records related to this study will be securely retained in a secure location for a period of 3 years after the

Effect of Platelet Rich Plasma Injections on Inflammatory and Chondrodegenerative Biomarkers
in Patients with Acute Anterior Cruciate Ligament Tears

[name].

Page 5 of 7

completion of the study or longer as required by law. At that time, all records will be properly destroyed.

8 Data Analysis

This study is anticipated to take 2 years to complete. All data will be entered into REDCap. The investigators will meet at appropriate intervals to evaluate and analyze the data.

9 Statistical Considerations

A power analysis was performed to determine sample size based upon recent clinical trials. Analysis utilized the average of standard deviation to detect average of group mean effect at 80% power. This determined that 25 patients per group would be needed to reach statistical significance. 10 additional patients will be account for potential patient withdrawal or lost-to-follow-up.

Ranges, means and standard deviations for all measures will be determined and calculated. Data will be analyzed for differences between groups using a t-test design, using a significant p-value of < 0.05 for rejecting the null hypothesis.

10 Quality Control and Assurance

All protocols will be monitored and analyzed data will be checked for accuracy by the principal investigator and /or a designated AREF research team member. All medical data will be kept in compliance with HIPAA guidelines.

11 Regulatory Requirements

Informed Consent:

The informed consent process will be performed by one of the study investigators or staff, in the office. All participants will have the study described to them and will give as much time as they require to read an approved, stamped version of the informed consent document. After signing of the informed consent document, participants will be given a copy for their records. This process will take place only after the patient has consented to proceed with the study.

Participant Confidentiality:

Participant confidentiality information is listed above in #7 (Data Management Procedures). All medical data will be recorded and stored in compliance with HIPAA guidelines.

12 References

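### Does aspirating both groups leave the trial unable to answer its objective about joint aspiration and PRP?

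*Combined protocol and SAP*

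**What the plan says.** Section 2 (Objectives) of the combined protocol and SAP says the trial is to "determine if an early intervention of joint aspiration and PRP injection will positively affect the biomarkers representative of chondral degeneration". The hypothesis follows: "We hypothesize that the intervention will reduce the volume of inflammatory and chondrodegenerative biomarkers following ACL injury". Neither sentence says what the intervention is compared with.

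The later sections do:

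- Section 4 (Participant Enrollment): after randomisation, participants will "be scheduled to receive either an injection of PRP or no injection in their involved knee".
- Section 5 (Study Design and Procedures), common to both arms: "Both groups will have joint aspirations performed at an initial visit, within the first 10 days after injury, and at the time of surgery".
- Section 5, control: "Group 1 will receive only joint aspirations as outlined above".
- Section 5, experimental arm: "Group 2 will undergo aspirations as outlined above and also receive a PRP injection at the initial visit and at a second visit".
- Section 9 (Statistical Considerations): "Data will be analyzed for differences between groups using a t-test design".

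The title names PRP injections alone as the treatment whose effect is studied. The background before Section 2 closes by calling for in vivo work on PRP, not on aspiration.

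**The concern.** Section 2 seems to define the intervention as aspiration plus PRP, yet the control group is aspirated too. Any effect of aspiration therefore drops out of the randomised comparison. There is no unaspirated arm. A before-and-after change within Group 2 would not recover the combined effect, because it would be mixed with the natural course after injury, and no such analysis is planned.

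What would be at stake is interpretation. If the objective were taken literally, a null result could be reported as showing that early aspiration with PRP does nothing, although both arms might have gained from aspiration. A positive result could be credited to the package when only one component had been tested.

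**Working it through.** **The plan's own figures.** Section 9 gives 25 per group plus 10 for withdrawal: 2 × 25 + 10 = 60, which matches Section 4. The 25 itself cannot be reproduced, since no effect size or SD is stated. Solving backwards at 80% power and two-sided 5% (sidedness is my assumption) gives d = (1.960 + 0.842) × √(2/25) = 0.79 by the normal approximation, or 0.81 for the t-test. None of this depends on how the objective is worded.

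**The contrast.** Let N be the natural course after injury, A the effect of the initial aspiration, and P the added effect of the PRP injections, as delivered, in a knee that has been aspirated.

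- Group 1 expectation: N + A
- Group 2 expectation: N + A + P
- Group 2 minus Group 1: (N + A + P) − (N + A) = P

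The most literal reading of Section 2 asks about A + P. The trial estimates P. Additivity is not needed, because P is defined given aspiration. The order of aspiration and injection at the initial visit, which Section 5 does not state, does not affect the cancellation either.

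**Illustration.** The documents give no value for A or P, so the values below are assumed, in SD units.

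| A | P | A + P | Group 2 − Group 1 | Chance of rejecting, 25 per group |
|---|---|---|---|---|
| 0 | 0 | 0 | 0 | 5% |
| 0.3 | 0 | 0.3 | 0 | 5% |
| 0.6 | 0 | 0.6 | 0 | 5% |
| 0 | 0.8 | 0.8 | 0.8 | 81% |
| 0.3 | 0.8 | 1.1 | 0.8 | 81% |
| 0.6 | 0.8 | 1.4 | 0.8 | 81% |

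The 81% is Φ(0.8 × √(25/2) − 1.960) = Φ(0.868) = 0.807. The last two columns do not move with A. The literal objective and the estimate differ by exactly A, while the test of PRP keeps its error rate and power whatever A is.

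**Which question do the documents pose?** Three points decide it.

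1. Section 2 does not say that the comparison is with an untreated or unaspirated knee. The conflict arises only if the reader supplies that comparator. With the control that Section 5 does supply, the objective becomes aspiration plus PRP against aspiration alone, which is what is randomised and tested.
2. The title, the close of the background, Section 4 and Section 5 all give the PRP contrast. None of them promises an estimate for aspiration or for the package.
3. Nowhere do the documents claim that aspiration by itself changes biomarkers. The background study of early treatment paired aspiration with a corticosteroid, so as described it does not isolate aspiration. Section 6 credits aspiration with better knee function, which is not the outcome here.

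**What rewording would change.** Writing the comparator into Section 2 would leave the arms, procedures, samples, test, sample size, estimate and p-value as they are.

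**The case for a change.** The best case for a change is that conclusions are judged against the objective and hypothesis, so these should name the contrast that was randomised. The hypothesis credits the intervention with lowering biomarkers and does not mention the other arm. The phrasing of the objective also mirrors the background's description of the corticosteroid study, which invites the reader to treat the combination as the thing tested. Adding a comparator costs a few words, and is more credible before results are known than after.

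Part of this stands. Section 2 does not name its comparator, no other section expressly corrects it, and the documents do not show that aspiration is inert. Naming the comparator would be tidier.

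The step from there to a defect in the plan does not stand. It is ordinary to name an experimental arm by everything it receives, and every add-on trial shares its background component in the same way. Here the shared component also supplies the fluid for the assays, and having it in both arms is what isolates PRP. To misreport the result, an author would have to pass over the title, the randomisation statement and the explicit description of the control group.

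**Conclusion.** The observation is correct and the concern does not hold. The trial estimates the effect of PRP injections added to aspiration, against aspiration alone, and says nothing about aspiration by itself or about the package against no treatment. That is a sound randomised comparison, and it is the one the title, background, Section 4 and Section 5 describe. Section 2 leaves its comparator unstated, which is a gap in wording that analysts and readers fill from the sections that follow.

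The effect on the estimate, p-value, error rate and sample size is zero. What remains is a small risk of loose wording in a report, which is met by describing the arms as Section 5 does. The conclusion rests on two points: Section 2 is read together with the later sections, and the only planned inference is the between-group test. If a report claimed an effect of aspiration or of the whole package, the literal reading would matter, but nothing in the plan calls for that claim. No change is needed.

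### The planned t-test names neither the first-aspirate value nor the known time from injury as a covariate; a prespecified ANCOVA would recover precision at almost no cost

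*Combined protocol and SAP*

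**What the plan says.** Section 2 sets out to "determine if an early intervention of joint aspiration and PRP injection will positively affect the biomarkers". Section 3 excludes patients with "an injury occurring more than 10 days before enrollment", so the injury date is needed for every patient at screening.

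Section 5 gives the sampling times. For the first sample it says "Both groups will have joint aspirations performed at an initial visit, within the first 10 days after injury". The second sample is taken when the patient has the operation, which may be up to 4 weeks from the injury. Group 2 will also "receive a PRP injection at the initial visit and at a second visit 5-12 days after the initial visit", so its first PRP dose falls within the same 10-day window.

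On allocation, section 4 says "The participants will then be randomly placed in one of the two study groups" and section 5 says "Patients will be randomized to 1 of 2 groups". Neither names a stratification factor or a method.

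Section 9 plans descriptive statistics and one inferential method: "Data will be analyzed for differences between groups using a t-test design". It does not say whether the surgery-time value or the change from the first aspirate is compared. It names no covariate, subgroup or sensitivity analysis.

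**The concern.** Every patient contributes two samples. The first carries information about the second because both come from the same knee, and a t-test on surgery-time values discards it. If the markers also change over the first 10 days, the first sample reflects the day the patient presented as well as the patient's own level. A t-test on change from the first sample would then carry that presentation effect into the comparison.

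Either way the treatment estimate is noisier than the collected data require. A difference between arms at the first aspirate that arises by chance is not corrected. With 25 patients per arm such differences are not rare, and the remedy uses only measurements and dates already in hand.

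**Working it through.** **The plan's own figure.** The total is consistent: 2 × 25 + 10 = 60. The 25 per group cannot be reproduced, because the biomarker, mean difference, SD and sidedness are not given. Solved backwards at two-sided 0.05 and 80% power, d = (1.960 + 0.842) × √(2/25) = 0.79, or 0.81 with the t distribution.

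**Chance imbalance in entry day.** Assume entry uniform over the integer days 0 to 10: variance (11² − 1)/12 = 10, SD 3.16 days. The difference in mean entry day between arms has SE 3.16 × √(2/25) = 0.89 days. It exceeds 1 day in 26% of trials and 2 days in 2.5%.

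**Validity.** In 40,000 simulated trials with 25 per arm, where entry day explained 0 to 40% of the outcome variance, the unadjusted t-test rejected a true null in 4.8% to 5.1%.

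**Precision: assumed inputs.** None of these is in the documents. Log-scale marker; between-patient SD 0.7 (variance 0.49); within-patient SD 0.5 (variance 0.25); k = ln 2/half-life, so k² = 0.0534, 0.0192 and 0.0048 per day² at 3, 5 and 10 days. Three settings for the surgery value:

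- A: it does not depend on time.
- B: the decline continues, with surgery on days 14 to 28 whatever the entry day (variance (15² − 1)/12 = 18.67).
- C: the decline continues, with surgery 10 to 18 days after entry (gap variance (9² − 1)/12 = 6.67).

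**Formulas.** Var(first) = 0.74 + 10k². Var(surgery) = 0.74 (A), 0.74 + 18.67k² (B), 0.74 + 16.67k² (C). Covariance = 0.49 (A, B) or 0.49 + 10k² (C).

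- t-test on surgery values: Var(surgery) × 2/25.
- ANCOVA on first value: [Var(surgery) − Cov²/Var(first)] × 2/25 × (1 + 1/46).
- Adding entry day: [Var(surgery | entry day) − 0.49²/0.74] × 2/25 × (1 + 2/45), where Var(surgery | entry day) drops the 10k² term in C.

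The last factors are the cost of estimating one or two covariates with 50 patients.

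**Worked case: A, 3-day half-life.** t-test: 0.74 × 0.08 = 0.0592. First value: (0.74 − 0.2401/1.274) × 0.08 × 1.022 = 0.0451. Plus entry day: (0.74 − 0.3245) × 0.08 × 1.044 = 0.0347. Ratios: 0.0592/0.0451 = 1.31; 0.0451/0.0347 = 1.30; overall 1.71.

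| Setting | Half-life | t-test | + first value | + entry day | Overall ratio | Added by entry day |
|---|---|---|---|---|---|---|
| A | 3 d | 0.0592 | 0.0451 | 0.0347 | 1.71 | +30% |
| A | 5 d | 0.0592 | 0.0394 | 0.0347 | 1.71 | +14% |
| A | 10 d | 0.0592 | 0.0356 | 0.0347 | 1.71 | +2% |
| B | 3 d | 0.1389 | 0.1265 | 0.1180 | 1.18 | +7% |
| B | 5 d | 0.0879 | 0.0688 | 0.0647 | 1.36 | +6% |
| B | 10 d | 0.0664 | 0.0429 | 0.0422 | 1.57 | +2% |
| C | 3 d | 0.1304 | 0.0659 | 0.0645 | 2.02 | +2% |
| C | 5 d | 0.0848 | 0.0459 | 0.0454 | 1.87 | +1% |
| C | 10 d | 0.0656 | 0.0370 | 0.0374 | 1.75 | −1% |
| No trend | – | 0.0592 | 0.0340 | 0.0347 | 1.71 | −2% |

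Simulations under the same SDs agree to within a few points. They gave 26% to 33% for entry day in A at 3 days, and up to 10% in B at 3 days.

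**If section 9 means change scores.** With no trend the variance is 2 × 0.25 × 0.08 = 0.0400, against 0.0347 for the full model (ratio 1.15). In A at 3 days it is (0.50 + 0.534) × 0.08 = 0.0827, worse than ignoring the first sample (0.0592).

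**The case against.** The strongest reply is that entry day does little. In setting A an unadjusted t-test on surgery values has variance 0.0592 at every half-life, so entry day does not touch it. In setting C entry day does affect it, but the first-aspirate value absorbs nearly all of that. The large figure for entry day needs a marker that falls quickly over 10 days and a surgery value unrelated to time, although surgery may fall anywhere up to 4 weeks. The documents neither name the biomarkers nor describe their course. All of this stands, and it is why entry day is only the secondary covariate here.

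It is also true that the plan has no validity fault on this point: randomisation balances entry day in expectation.

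A reader might infer more than the documents support:

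- **That the wide window biases the comparison.** It does not; the cost is variance and chance imbalance.
- **That an entry-day imbalance moves the result whatever the endpoint.** In setting A it moves change scores but not surgery values; in setting C the reverse. Section 9 does not say which is analysed.
- **That the plan treats first aspirates from different days as comparable baselines.** It never calls the first aspirate a baseline or states its use.
- **That the trial fails to show whether earlier treatment works better.** Section 2 does not ask that question, and no early-versus-late comparison is planned.
- **That randomisation must be stratified by entry day.** Nothing in the documents supports a particular cut, and the continuous covariate does most of the work.

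What the reply does not answer is the loss from leaving out the first-aspirate value, which does not depend on any kinetics.

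**Conclusion.** The point holds as a modest, inexpensive improvement. The stated analysis names no use of the first-aspirate value or the time from injury. Under the assumed SDs, the two-covariate ANCOVA lowers the variance of the treatment estimate about 1.2- to 2.0-fold against a t-test on surgery values. That is equivalent to analysing 25 × 1.2 = 30 to 25 × 2.0 = 50 patients per arm.

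Most of this comes from the first-aspirate value, and nearly all of it outside the 3-day half-life in settings A and B. Entry day adds about −2% to +10% if the time course continues to surgery, and up to about 30% only in the most favourable setting. The SDs, half-lives, entry days and surgery days are all assumptions. A weaker within-patient correlation than the assumed 0.49/0.74 = 0.66 would shrink the main gain.

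**What to change.** In section 9, replace the t-test with a prespecified ANCOVA: log surgery-time biomarker as outcome, with group, log first-aspirate value and days from injury to first aspirate (continuous) as terms. Report the adjusted group difference with its 95% confidence interval. Fix the model before the stored samples are assayed, so that the covariates cannot be chosen on the results.

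Two conditions should be stated. The first-aspirate value is a proper covariate only if that sample is drawn before any PRP is injected, and section 5 does not give the order. Section 4 places allocation before the visit is scheduled, so the date of the first aspirate should not depend on the group; if that cannot be assured, days from injury to enrolment can be used instead.

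The cost is one or two degrees of freedom, slightly more analysis work, and about 2% of variance for the entry-day term if the markers are flat. No visits, samples or patients are added, and the visit and treatment windows stay as they are. Stratifying randomisation by early versus late presentation is optional and not needed.

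### Only Group 2 has plasma added to the sampled joint, and no fluid volume is planned to be recorded, so dilution or carry-over cannot be told apart from a biomarker effect

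*Combined protocol and SAP*

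**What the plan says.** **Injected fluid.** Section 5 (Study Design and Procedures) gives PRP to Group 2 only; those patients "also receive a PRP injection at the initial visit and at a second visit 5-12 days after the initial visit". For the control arm it says "Group 1 will receive only joint aspirations as outlined above", and section 4 describes the two options as to "receive either an injection of PRP or no injection in their involved knee". No saline or sham injection balances the added fluid.

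**Sampling times.** Both arms have "joint aspirations performed at an initial visit, within the first 10 days after injury", and again "at the time of surgery, within 4 weeks of injury". The surgery sample has a latest day but no earliest day, and no interval after the second injection is stated.

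**Measurement.** Section 2 hypothesises that "the intervention will reduce the volume of inflammatory and chondrodegenerative biomarkers following ACL injury". Section 5 (Biomarker Analysis) says "Enzyme-linked immunosorbent assay kits will be used to assess chondrodegenerative & synovial fluid biomarkers". No marker is named, and no unit, normalisation or dilution correction is given. Aspirated volume and injected volume are not mentioned. The PRP is sampled for cell count only.

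**Analysis.** Section 9 plans a between-group t-test at 0.05 on means and standard deviations. It plans no transformation and no adjustment for fluid volume or time since injection.

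**The concern.** A concentration is an amount divided by a fluid volume, and treatment can change either. In Group 2 the volume may change in two ways: injected plasma may still be in the joint at surgery, and section 6 warns of joint inflammation after PRP, which could alter the effusion. Randomisation does not protect against this, because the difference arises after allocation and in one arm only.

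The direction depends on the marker. Extra fluid free of the marker lowers its concentration, as the hypothesis predicts. A marker that PRP itself contains could be carried over, which raises its concentration and could hide a benefit. Since no marker is named, the documents do not show which would dominate. A significant t-test could then be read as less cartilage breakdown when only the fluid changed. A volume not noted at the aspiration cannot be recovered later.

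**Working it through.** **1. The plan's own figure.** Section 9 gives 25 per group at 80% power but no difference or SD, so it can only be solved backwards. Normal approximation, two-sided 0.05: d = √(2/25) × (1.960 + 0.842) = 0.79; with the t distribution, 0.81. Sidedness is not stated, so two-sided is assumed. The total agrees: 50 + 10 = 60.

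**2. Timing (section 5, days after injury).**
- Earliest second injection: 0 + 5 = day 5. Latest: 10 + 12 = day 22.
- Surgery by day 28. Longest possible gap: 28 − 5 = 23 days. For the latest permitted injection: at most 28 − 22 = 6 days.
- Shortest gap: not bounded. No text says that the second injection must come before surgery.

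**3. Dilution model.** Let native fluid be S, residual marker-free plasma V, and f = V/(S + V). With no biological effect the Group 2 concentration is (1 − f) times what it would have been. On the raw scale the standardised shift is d = f / {CV × √[(1 + (1 − f)²)/2]}.

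Assume lognormal data with log-SD 0.8, so CV = √(e^0.64 − 1) = 0.95. Then:
- f = 10%: d = 0.10/(0.95 × 0.951) = 0.11
- f = 20%: d = 0.20/(0.95 × 0.906) = 0.23
- f = 30%: d = 0.30/(0.95 × 0.863) = 0.37

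Simulated rejection rates of the untransformed t-test, 25 per group, two-sided 0.05, no biological effect, the same f for every Group 2 patient:

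| Assumed log-SD | f = 10% | f = 20% | f = 30% |
|---|---|---|---|
| 0.5 | 10% | 31% | 65% |
| 0.8 | 6% | 13% | 27% |
| 1.0 | 5% | 9% | 16% |

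With f at 0 or 2% and log-SD 0.8 the rate is 4.4%, in effect the nominal 5%. If the data were log-transformed, which section 9 does not plan, the log-SD 0.8 row would be 7%, 16% and 34%.

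**4. Does recovered amount help?** Let C be the undiluted concentration. Under pure dilution, concentration × volume = C(1 − f) × S/(1 − f) = CS, so f cancels if aspirated volume tracks joint volume. Two decision rules were compared on the log scale, with log-SD 0.8 and an assumed independent log-volume SD of 0.6:
- Requiring only that concentration and amount point the same way: false reductions fall from 16% to 15% at f = 20%, and from 34% to 30% at f = 30%. Both measures contain the same concentration values, so they agree largely by construction.
- Judging the difference in amount by its own confidence interval: false reductions stay at about 2.5% (one-sided).

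The price is noise. The log-SD of amount is √(0.8² + 0.6²) = 1.0, so a standardised effect of 0.81 on concentration shrinks to 0.81 × 0.8 = 0.65 on amount.

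**The case against.** The strongest objection is that the size rests wholly on assumption. Injected volume, effusion volume, clearance and SD are all absent. A constant f is crude when gaps of up to 23 days are permitted, and the day-22 injection is the extreme corner of the windows. If the plasma has cleared by surgery, dilution bias is close to nil. All of this stands: the documents show that bias is possible, not how large it is.

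It is also fair that a short protocol's silence does not prove that volumes go unrecorded. Section 7 sends all data collected to REDCap, but no field list is shown, and days since injection could be derived if the dates are captured. The point is that the plan does not require any of this.

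A third objection is that recovered amount is itself flawed. Aspiration may not empty the joint, and PRP may change effusion volume, so the product could mask a real fall in concentration. This stands too, and limits that analysis to a supportive role.

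Two stronger readings are tempting. A reader might infer that the endpoint is stated to be a concentration; that is only an inference from the assay. A reader might also infer that all leftover PRP is discarded. The sentence ending "will be disposed of through standard biohazard waste disposal systems" concerns the unused portion of a sample and follows directly after the 0.1–0.5 mL cell-count sample. How much would remain for an assay is not shown.

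**Conclusion.** The structural gap is certain from the text: fluid is added in one arm only, no gap before the outcome sample is stated, the hypothesis is worded in a different quantity from the one the assay probably reads, and no volume is planned to be recorded. As written, the trial could not separate a change in joint fluid from a change in the biomarker.

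The size is not known. The rates of 6%, 13% and 27% illustrate residual shares of 10%, 20% and 30% at log-SD 0.8 and are not predictions for this trial; near-zero residual plasma gives about 5%. A reader might infer from them that a positive result would probably be an artefact. The documents do not support that, because they give nothing from which f or the SD can be set. This is a worthwhile, cheap improvement to interpretability. It does not show that the comparison is invalid.

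**What to change.** 1. **Section 5.** Record in REDCap the volume aspirated at both aspirations in both arms, the PRP volume injected at each visit, and the dates of injection and surgery.
2. **Section 9.** Define the endpoint and its unit as concentration. Add a prespecified sensitivity analysis of the between-group difference in recovered amount (concentration × aspirated volume) with its confidence interval, and a display of Group 2 concentration by days since last injection.
3. **Interpretation rule.** If concentration falls but the interval for recovered amount does not show a clear reduction, report that dilution cannot be excluded. Do not rely on the two measures pointing the same way.
4. **Optional.** Assay leftover PRP for the same markers, if enough remains, to bound carry-over.

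Section 5 should also reconcile the second-injection and surgery windows with each other; no interval is proposed here.

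The cost is a few data fields, one analysis and one display, with no extra patient procedure. The downside is that aspirated volume is an imperfect, noisy measure of joint fluid and may itself respond to treatment. The amount analysis is therefore supportive only, and it will sometimes be inconclusive when PRP has a real effect.
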